6.4. Immunogenicity Analysis

The analyses of immunogenicity will be based on the PP Set and will be by baseline serostatus group (ie, flavivirus-seropositive, flavivirus-seronegative groups, flavivirus-serostatus missing, and overall) and vaccination group as defined in Section 6.1. Subgroup analysis based on age group (>=18 and < 50 years, >= 50 and <=65 years), gender and region may be performed. If the number of participants in the FAS and PP Set differ (defined as the difference divided by the total number of participants in the PP Set) by more than 10% (for each serostatus group), supportive analyses of antibody-mediated immunogenicity may be conducted using the FAS. The supportive analysis is required if the condition is met at end of study; it is optional for the interim analyses.

The GMT/GMC and geometric mean (GM) level will be calculated using the following formula:

$$10^{\left\{\frac{\sum_{i=1}^{n}\log_{10}(t_{i})}{n}\right\}}$$

where $t_1, t_2, ..., t_n$ are *n* observed immunogenicity titers or levels.

The geometric mean fold-rise (GMFR) measures the changes in immunogenicity titers or levels within subjects. The GMFR will be calculated using the following formula:

$$10^{\left[\sum_{i=1}^{n}\log_{10}\left(\frac{v_{ij}}{v_{ik}}\right)\right]} = 10^{\left[\sum_{i=1}^{n}\log_{10}\left(v_{ij}\right) - \log_{10}\left(v_{ik}\right)\right]}$$

where, for *n* subjects, v_{ij} and v_{ik} are observed immunogenicity titers or levels for subject *i* at time points *j* and *k*, $j \neq k$

6.4.1. Immunogenicity Assessments

There will be two types of immunogenicity assessments:

- Antibody-mediated immunogenicity assessments include ZIKV-specific nAbs, as measured by PRNT, MN, and ZIKV-specific bAbs, as measured by ligand binding assay.
- CMI assessments include ZIKV-specific T cells as measured by intracellular
 cytokine staining assay and sequencing and ZIKV-specific B cells as measured by
 ELISpot. Blood specimen for CMI will be collected for a subset of participants with
 seropositive or seronegative status at baseline.

6.4.2. Primary Analysis of Antibody-Mediated Immunogenicity Endpoints

For each group, the following evaluations will be performed at Day 57, or at each time point at which blood samples are collected for antibody-mediated immunogenicity (unless otherwise specified):

 GMT of ZIKV-specific nAbs, in all participants, in initially flavivirus-seronegative, and in initially flavivirus seropositive- participants, as measured by PRNT, will be provided at Day 57 with corresponding 95% CI. The 95% CIs will be calculated based on the t-distribution of the log-transformed values then back transformed to

- the original scale for presentation. The following descriptive statistics will also be provided at Day 57: the number of subjects (n), median, minimum and maximum.
- Proportion of participants with seroconversion in ZIKV-specific nAbs from Day 1 to Day 57, as measured by PRNT will be tabulated with 2-sided 95% Clopper-Pearson CIs. The difference of the seroconversion rates between each mRNA-1893 group and placebo group will be provided with 2-sided 95% CIs using the Miettinen-Nurminen method.
- For ZIKV-specific nAb titers, the GMT at Day 57 for each vaccination group, and the ratio of GMT of mRNA-1893 μg (2-dose), mRNA-1893 μg (2-dose), mRNA-1893 μg (single-dose) vs. Placebo respectively, will be estimated based on an analysis of covariance (ANCOVA) model that will be carried out for flavivirus-seropositive groups and flavivirus-seronegative groups separately using the PP Set. The dependent variable will be the nAb at Day 57 with the vaccination group as a factor and the baseline values as covariate (if applicable, ie, for flavivirus-seropositive groups only). The GMT and corresponding 95% CI for each vaccination group, and the ratio of GMT of mRNA-1893 μg (2-dose), mRNA-1893 μg (single-dose) vs. Placebo respectively, together with corresponding 95% CI will be provided.

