4.2. Scientific Rationale for Study Design

The design and dose levels proposed for this study (Study mRNA-1893-P201) are based on accumulated safety and immunogenicity data from the Phase 1 Study mRNA-1893-P101, which involved a total of 120 participants. Group unblinding interim analyses performed at Day 57 (ie, 28 days after the second vaccination) showed a safety profile compatible with a large use of the vaccine candidate and a production of ZIKV-specific nAbs at an SCR ranging from 12.5% (2.7% - 32.4%) to 75% (53.3% - 90.2%) after 1 vaccine administration and from 86.4% (65.1% - 97.1%) to 100% (85.8% - 100%) after the complete 2-dose vaccine administration.

Study mRNA-1893-P201 is intended to confirm the safety and immunogenicity trends observed during the Phase 1 study and aims to select the dose level for the Phase 3 program. Two dose levels, and µg and µg, have been chosen as they appear to give the optimal response at Day 57 in terms of geometric mean titers (GMTs) and SCRs with a similar safety profile. The number of participants (200 per treatment arm with approximately 100 participants per baseline flavivirus serostatus in each treatment arm) planned for enrollment is consistent with a Phase 2 stage clinical study. The collection of solicited ARs and unsolicited AEs following vaccination is consistent with vaccine evaluation studies. Additionally, the 2-year follow-up will provide long-term safety profile information and documentation on the duration of the ZIKV-specific nAb response after a 1- or 2-dose regimen. It may also give the opportunity to evaluate occurrence of flavivirus infections,

ModernaTX, Inc.
Protocol: mRNA-1893-P201, Amendment 3

mostly ZIKV and dengue, as the excontinental US sites are areas with potential for flavivirus circulation. The collection of blood at the given time points and the selection of the assays for the assessment of the ZIKV-specific immune response are based on experience from the preclinical and previous clinical studies.

09 Dec 2021

mRNA-1893

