For calculation regarding antibody titers/antibody concentrations, antibody values reported as below LLOQ will be replaced by 0.5 × LLOQ. Values that are greater than the upper limit of quantification (ULOQ) will be converted to the ULOQ. Missing results will not be imputed.

The following stages for safety analyses will be used in this study:

- Up to 28 days after any vaccination: this stage starts at the day of each vaccination
 and continue through the earliest date of (the day of each vaccination and 27
 subsequent days, next vaccination [if applicable]). This analysis period will be used
 as the primary analysis period for safety analyses including unsolicited AE, except
 for solicited AR, unless specified otherwise.
- Up to 28 days after the first vaccination.
- Up to 28 days after the second vaccination.
- Overall stage: this analysis period starts at the first injection on Day 1 and continues through the earliest date of (study completion, discontinuation from the study, or death).

Unscheduled visits: Unscheduled visit measurements will be included in analysis as follows:

- In scheduled visit windows per specified visit windowing rules.
- In the derivation of baseline/last on-treatment measurements.
- In the derivation of maximum/minimum on-treatment values and maximum/minimum change from baseline values for safety analyses.
- In individual subject data listings as appropriate.

Visit windowing rules: The analysis visit windows for protocol-defined visits are provided in Appendix B.

Incomplete/missing data:

- Imputation rules for missing prior/concomitant medications, non-study vaccinations and procedures are provided in Appendix C.
- Imputation rules for missing AE dates are provided in Appendix D.
- For laboratory assessments, if majority of results are indefinite, imputation of these values will be considered. If the laboratory results are reported as below the LLOQ (e.g., <0.1), the numeric values will be imputed by 0.5 × LLOQ in the summary. If the laboratory results are reported as greater than the ULOQ (e.g., >3000), the numeric values will be imputed by ULOQ in the summary.
- Other incomplete/missing data will not be imputed, unless specified otherwise.

Treatment groups:

The following vaccination groups will be used for summary purposes:

- mRNA-1893 vaccine: μg (2-dose)
- mRNA-1893 vaccine: CCI μg (2-dose)
- mRNA-1893 vaccine: μg (single-dose)
- mRNA-1893 vaccine: Total
- Placebo

Summary by flavivirus serostatus:

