All analyses and data summaries/displays will be provided by flavivirus serostatus (flavivirus-seropositive, flavivirus-seronegative, and/or overall) unless otherwise specified,

please also refer to Section 6.5 Planned Analyses. Baseline flavivirus status is determined by serology testing.

A participant is baseline seronegative if at least three baseline serology testings (dengue IgG, dengue IgM, West Nile IgG and West Nile IgM) are negative, and none of the serology testings is positive. If at least one of the baseline serology testings is positive, the participant is baseline seropositive. If two or more of the serology testings are "missing" or "unknown", and none of the serology testings is positive, the baseline serostatus will be "unknown" or "missing". A single testing result of "equivocal" is considered as "unknown", regardless of the numeric values.

All analyses will be conducted using SAS Version 9.4 or higher.

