6.4.3. Secondary Analysis of Antibody-Mediated Immunogenicity Endpoints

- GMT of ZIKV-specific nAbs, in all participants, in initially flavivirus-seronegative, and in initially flavivirus seropositive- participants, as measured by PRNT and MN, will be provided at Days 1, 8, 29, 36, and 57 (Day 57 only for MN) with corresponding 95% CI. The 95% CIs will be calculated based on the t-distribution of the log-transformed values then back transformed to the original scale for presentation. GMT and corresponding 95% CI will be plotted over time. The following descriptive statistics will also be provided at each time point: the number of subjects (n), median, minimum and maximum.
- GMFR of ZIKV-specific nAbs, in all participants, in initially flavivirus-seronegative, and in initially flavivirus seropositive- participants, as measured by PRNT and MN at Days 8, 29, 36, and 57 over pre-vaccination (eg, Visit Day 1 [baseline]) will be tabulated with 95% CI. The 95% CIs will be calculated based on the t-distribution of the difference in the log-transformed values then back transformed to the original scale for presentation. GMFR and corresponding 95% CI will be plotted over time.

- The geometric mean ratio (GMR) with 95% CI for treatment difference on the ZIKV-specific nAbs titers between each mRNA-1893 group vs. placebo will be provided at Days 8, 29, 36, and 57. The 95% CI will be calculated using t-distribution for the mean difference in the log scale, and then transformed back to the original scale.
- Proportion of participants with seroconversion in ZIKV-specific nAbs from Day 1 (baseline) to Days 8, 29, 36, and 57 (only for MN), as measured by PRNT and MN will be tabulated with 2-sided 95% Clopper-Pearson CIs. The difference of the seroconversion rates between each mRNA-1893 group and placebo group will be provided with 2-sided 95% CIs using the Miettinen-Nurminen method.
- Proportion of initially flavivirus-seronegative participants with seroresponse in ZIKV-specific nAb titer at Days 8, 29, 36, and 57 (Day 57 only for MN), as measured by PRNT and MN will be tabulated with 2-sided 95% Clopper-Pearson CIs.
- Proportion of initially flavivirus-seropositive participants with a ≥2-fold or 4-fold increase in ZIKV-specific nAb titers from Visit Day 1 (baseline) to Days 8, 29, 36, and 57, as measured by PRNT, MN will be tabulated with 2-sided 95% Clopper-Pearson CIs.

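### In seronegatives, the Day 57 model pools one variance over vaccine and placebo arms, so its 95% intervals are modestly miscalibrated if most placebo titers fall below LLOQ

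*SAP*

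**What the plan says.** SAP 6.4.2 plans two kinds of interval for the Day 57 PRNT titer.

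- **Arm-wise GMT**, in all participants and in each serostatus group: "The 95% CIs will be calculated based on the t-distribution of the log-transformed values".
- **Model GMT and ratio to placebo**, from an "analysis of covariance (ANCOVA) model that will be carried out for flavivirus-seropositive groups and flavivirus-seronegative groups separately using the PP Set". Its terms are given as "with the vaccination group as a factor and the baseline values as covariate (if applicable, ie, for flavivirus-seropositive groups only".

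SAP 6.4.3 adds a Day 57 ratio to placebo as a secondary analysis: "The 95% CI will be calculated using t-distribution for the mean difference in the log scale".

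Two rules in SAP 6.1 shape the seronegative data. For titers, "antibody values reported as below LLOQ will be replaced by 0.5 × LLOQ". Serostatus comes from dengue and West Nile serology, not from the Zika titer: "A participant is baseline seronegative if at least three baseline serology testings (dengue IgG, dengue IgM, West Nile IgG and West Nile IgM", with none of the tests positive.

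SAP 6.4 mentions no unequal-variance model, robust standard error or censoring method. The sensitivity analysis in 6.4.6 is optional and uses the same methods.

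**The concern.** Without the baseline covariate, the seronegative model is a one-way comparison of four arms, and the ANCOVA default is a single residual variance. An arm whose values are nearly all the same substituted constant contributes almost no variance. It pulls the pooled estimate below the true vaccine-arm variance and far above the placebo variance.

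The vaccine arms need not share a variance either. Across the four Phase 1 dose levels, Protocol 4.2 reports an "SCR ranging from 12.5% (2.7% - 32.4%) to 75% (53.3% - 90.2%) after 1 vaccine administration". With two doses the rates were 86.4% to 100%. An arm that mixes responders and non-responders can be much more variable than one where nearly everyone responds.

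At stake are the error bars on a primary immunogenicity endpoint in about half the trial, at the Day 57 analysis that SAP 6.6 makes the ground for moving to Phase 3.

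**Working it through.** **Inputs.** About 100 seronegatives per arm (SAP 4.3). Values below LLOQ are constant (SAP 6.1). The following are not in the documents and are assumed: a log10 scale for the model (6.4.2 does not state one), a vaccine-arm SD of 0.5 log10, and the placebo distribution. The width factors below do not depend on the SD.

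**Formulas.** Set the two-dose variance to 1, the one-dose variance to c and the placebo variance to d. With equal arm sizes the pooled variance is MSE = (2 + c + d)/4. Model width divided by correct width, f, is:

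- two-dose GMT: √MSE
- one-dose GMT: √(MSE/c)
- two-dose ratio: √(2·MSE/(1 + d))
- one-dose ratio: √(2·MSE/(c + d))

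Coverage is approximately P(|Z| < 1.96·f).

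**Nominal level.** With c = d = 1, MSE = 1 and every factor is 1, giving 95%. Simulation of the pooled model with equal variances gave 94.8% to 95.5%.

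**Constant placebo, equal vaccine variances (c = 1, d = 0).** MSE = 0.75.

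- Vaccine GMT: f = √0.75 = 0.87; 1.96 × 0.866 = 1.70; coverage 91.0%.
- Ratio to placebo: f = √1.5 = 1.22; 1.96 × 1.225 = 2.40; coverage 98.4%.

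Simulation (20,000 trials, 100 per arm) gave 90.9–91.1% and 98.3–98.4%. Results at 60 and 130 per arm were essentially the same.

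**Some placebo titers above LLOQ** (averaging 0.6 log10 above the floor). With 5%, 10% and 20% above LLOQ, vaccine GMT coverage is about 92% to 93%. Ratio intervals are 1.18, 1.16 and 1.12 times too wide.

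**Unequal vaccine variances, constant placebo** (simulated coverage):

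| One-dose variance ÷ two-dose variance | MSE | One-dose GMT | Two-dose GMT | One-dose ratio |
|---|---|---|---|---|
| 0.5 | 0.625 | 97% | 88% | over 99% |
| 1 | 0.75 | 91% | 91% | 98% |
| 2 | 1.00 | 83% | 95% | 95% |
| 3 | 1.25 | 80% | 97% | 92% |

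The one-dose ratio interval becomes too narrow once c + d exceeds 2. At c = 3, f = √(2.5/3) = 0.91.

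**Illustration with Phase 1 rates.** Take two-dose arms with 95.5% and 100% responders (two of the rates in Protocol 2.2.2). Assume responders lie 1.5 log10 above the floor after two doses and 1.0 after one, with SD 0.4. One-dose GMT coverage is then 87%, 86% and 96% at 75%, 50% and 12.5% one-dose responders. Two-dose GMT coverage runs from 85% to 96%, and ratio coverage from 96% to over 99%.

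**Absolute size** at SD 0.5, constant placebo, equal vaccine variances. The pooled SD is 0.5 × 0.866 = 0.433.

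- GMT limits: 10^(1.966 × 0.433/10) = a factor of 1.22. Arm-wise: 10^(1.984 × 0.5/10) = 1.26.
- Ratio limits: 10^(1.966 × 0.433 × √0.02) = a factor of 1.32. The correct factor is 1.26, because constant placebo adds no variance.

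**Arm-specific variances.** In the equal-variance vaccine scenario with constant placebo, arm-wise t and Welch intervals cover 94.9% to 95.4% and HC3 intervals 94.8% to 95.3%. The HC3 half-width for a GMT is 1.966·s/√99 = 0.1976s, against 1.984·s/√100 = 0.1984s for the arm-wise t, a difference of 0.4%.

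**The case against.** The strongest reply is that nothing important turns on this. SAP 4.2 rules out hypothesis testing, and no decision rule uses these intervals. A factor of 1.22 against 1.26, or 1.32 against 1.26, is minor beside the 4-fold effect in Protocol 9.2. In the equal-variance case the ratio error is conservative. The arm-wise t interval in 6.4.2 is already calibrated for the vaccine arms. So, at equal arm sizes, is the 6.4.3 ratio interval: pooled and Welch two-sample standard errors then coincide. All of this stands, and it sets the severity.

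It does not remove the point. The Day 57 ratio under the primary-analysis heading comes from the pooled model, and its error is not always conservative.

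A second reply is that the placebo distribution is assumed. That is also correct. Dropping the baseline covariate only in seronegatives suggests the authors expected little Zika titer there. But serostatus rests on other flaviviruses, so some placebo titers may exceed LLOQ. The error then shrinks but remains.

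A third reply is that arm-specific variances have a cost, which also stands. They do not cure skewness: coverage is about 93% for an arm with 12.5% responders, where the pooled model covers about 96% for the GMT. For the placebo GMT they cover about 90% to 94% with 5% to 20% above LLOQ. The pooled interval covers about 100% there, because it is far too wide.

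**Conclusion.** The point holds at low severity. As written, the seronegative model gives miscalibrated 95% intervals if placebo is mostly below LLOQ. The central estimate is about 91% coverage for vaccine GMTs and 98% for ratios. Both depend on the variances: a one-dose arm with 3 times the two-dose variance has about 80% and 92%. These figures rest on 100 per arm, a log10 scale, the default pooled variance and assumed titer distributions.

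A reader might infer more than the documents support:

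- **That the lead GMT interval cannot be identified.** No sentence names it. However, SAP 3.1 defines the endpoint in all participants and both serostatus groups, and only the arm-wise t interval covers all three. Protocol 9.4.4 plans only descriptive GMTs with a 95% CI. Naming the interval is mostly a missing detail.
- **That a model placebo GMT limit of about 0.41 × LLOQ (0.5/1.22) is impossible.** The 0.5 × LLOQ floor is a substituted value, and true titers can be lower.
- **That the seropositive model is equally affected.** It carries a baseline covariate, and no calculation here covers it.
- **That the move to Phase 3 is compromised.** The absolute differences are too small, and no rule is tied to the intervals.

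**What to change.** In SAP 6.4.2, for the seronegative stratum only:

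1. State that the model is on the log10 scale and that its intervals for the GMTs and the ratios to placebo use arm-specific variances, either HC3 standard errors or Welch/Satterthwaite. HC3 still runs when the placebo variance is zero.
2. Keep the pre-specified arm-wise t interval as the lead interval for the vaccine-arm GMTs, consistent with the all-participants analysis. Name the unequal-variance interval as the lead for the ratio to placebo.
3. For placebo, report the number of titers above LLOQ, and do not rely on the GMT interval when few exceed it.

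The cost is one model option and a few sentences, with a negligible loss of precision if the variances turn out equal. The remaining weakness is skewness in arms with few responders, which this change does not address.

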6.4.3. Secondary Analysis of Antibody-Mediated Immunogenicity Endpoints

- GMT of ZIKV-specific nAbs, in all participants, in initially flavivirus-seronegative, and in initially flavivirus seropositive- participants, as measured by PRNT and MN, will be provided at Days 1, 8, 29, 36, and 57 (Day 57 only for MN) with corresponding 95% CI. The 95% CIs will be calculated based on the t-distribution of the log-transformed values then back transformed to the original scale for presentation. GMT and corresponding 95% CI will be plotted over time. The following descriptive statistics will also be provided at each time point: the number of subjects (n), median, minimum and maximum.
- GMFR of ZIKV-specific nAbs, in all participants, in initially flavivirus-seronegative, and in initially flavivirus seropositive- participants, as measured by PRNT and MN at Days 8, 29, 36, and 57 over pre-vaccination (eg, Visit Day 1 [baseline]) will be tabulated with 95% CI. The 95% CIs will be calculated based on the t-distribution of the difference in the log-transformed values then back transformed to the original scale for presentation. GMFR and corresponding 95% CI will be plotted over time.

- The geometric mean ratio (GMR) with 95% CI for treatment difference on the ZIKV-specific nAbs titers between each mRNA-1893 group vs. placebo will be provided at Days 8, 29, 36, and 57. The 95% CI will be calculated using t-distribution for the mean difference in the log scale, and then transformed back to the original scale.
- Proportion of participants with seroconversion in ZIKV-specific nAbs from Day 1 (baseline) to Days 8, 29, 36, and 57 (only for MN), as measured by PRNT and MN will be tabulated with 2-sided 95% Clopper-Pearson CIs. The difference of the seroconversion rates between each mRNA-1893 group and placebo group will be provided with 2-sided 95% CIs using the Miettinen-Nurminen method.
- Proportion of initially flavivirus-seronegative participants with seroresponse in ZIKV-specific nAb titer at Days 8, 29, 36, and 57 (Day 57 only for MN), as measured by PRNT and MN will be tabulated with 2-sided 95% Clopper-Pearson CIs.
- Proportion of initially flavivirus-seropositive participants with a ≥2-fold or 4-fold increase in ZIKV-specific nAb titers from Visit Day 1 (baseline) to Days 8, 29, 36, and 57, as measured by PRNT, MN will be tabulated with 2-sided 95% Clopper-Pearson CIs.

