4.4. Randomization

The randomization will be done in a blinded manner using a centralized Interactive Response Technology (IRT), in accordance with pre-generated randomization schedules. Approximately 800 participants will be randomized in parallel according to a 1:1:1:1 randomization ratio to the 4 treatment arms. Randomization was initially stratified by participants' baseline flavivirus serostatus using a point of care assay under the original protocol (dated 21 February 2021). Under the protocol amendment 1 (16 September 2021), protocol amendment 2 (27 October 2021) and current Amendment 3 (09 December 2021), randomization will be stratified only by participants' region (continental US and Puerto Rico). Only the unblinded pharmacy personnel (Section 4.5) will have controlled access to which arm the participant is randomly assigned.

Blinding and Unblinding This is an observer-blind study. The investigator, study staff, study participants, site monitors, and Sponsor personnel (or its designees) will be blinded to the IP administered until the electronic data capture (EDC) is locked and clinical study report (CSR) has been written, with certain exceptions, please refer to Section 6.3.2 of the protocol for details.

Study site blinded staff will remain blinded to individual treatment assignments until the end of the study.

Except in the case of medical necessity, a participant's treatment assignment should not be unblinded without the approval of the Sponsor. If a participant becomes seriously ill or pregnant during the study, the blind will be broken only if knowledge of the treatment assignment will affect that participant's clinical management. In the event of a medical emergency requiring identification of individual treatment assignment, the investigator will make every attempt to contact the Sponsor medical lead or designee to explain the need for unblinding within 24 hours of opening the code. The investigator will be responsible for documenting the time, date, reason for unblinding, and the names of the personnel involved. The investigator (or designee) will have access to unblind participants within IRT. All unblindings will be tracked via an audit trail in IRT and documented in the final study report.

The Sponsor will remain blinded to IP assignment throughout the treatment phase for each individual treatment arm of the study up until the specified time point for interim analysis (IA), as outlined in Section 6.6.

5. Analysis Populations

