6.3.1.5. Solicited Adverse Reactions

All summary tables for solicited ARs will be provided by baseline flavivirus serostatus (flavivirus-seropositive, flavivirus-seronegative, and/or overall).

An AR is any AE for which there is a reasonable possibility that the test product caused the AE. The term "Solicited Adverse Reactions" refers to selected signs and symptoms occurring after injection administration during a specified post-injection follow-up period (day of injection and 6 subsequent days). The solicited ARs are recorded by the subject in eDiary. The occurrence and intensity of selected signs and symptoms is actively solicited from the participant during a specified post-injection follow-up period (day of injection and 6 subsequent days), using a pre-defined checklist in the eDiary (i.e., solicited ARs).

The following local ARs will be solicited: pain at injection site, erythema (redness) at injection site, swelling (hardness) at injection site.

The following systemic ARs will be solicited: headache, fatigue, myalgia (muscle aches all over the body), arthralgia (aching in several joints), nausea/vomiting, fever, and chills.

The solicited ARs will be graded based on the grading scales presented in Table 13 in the protocol, modified from the Toxicity Grading Scale for Healthy Adult and Adolescent Volunteers Enrolled in Preventative Vaccine Clinical Trials (DHHS 2007). Investigator will assess Grade 4 events (with exception of fever).

If a solicited local or systemic AR continues beyond 7 days post injection, the participant will be prompted to capture solicited local or systemic AR in the eDiary until resolution.

All solicited ARs (local and systemic) will be considered causally related to vaccination.

All solicited ARs analyses will be based on Solicited Safety Set. All solicited ARs analyses will be provided by flavivirus serostatus and vaccination group as defined in Section 6.1 for each vaccination (first, second), unless otherwise specified.

The number and percentage of subjects who reported any solicited AR, any solicited local AR, and any systemic solicited AR during the 7-day follow-up period after each vaccination will be tabulated by flavivirus serostatus, vaccination group, and vaccination,

with a two-sided 95% exact CI using the Clopper-Pearson method. The same analysis will be conducted for subgroups defined by region (United States and Puerto Rico).

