6.4.5. Analysis of CMI Endpoints

The CMI assessments will be performed with the additional blood samples collected for peripheral blood mononuclear cells (PBMC) isolation from the CMI subset participants, the analysis details will be provided in a separate document.

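### The SAP plans no adjusted all-participant GMT ratio versus placebo; the overall ratio has an unadjusted interval that is valid but may be wider than it needs to be

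*SAP*

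**What the plan says.** SAP 6.4.3 provides the GMR for each mRNA-1893 group against placebo at Days 8, 29, 36 and 57. It names no covariate: "The 95% CI will be calculated using t-distribution for the mean difference in the log scale". That bullet does not itself mention an overall ratio. The overall ratio follows from SAP 6.4, which sets the reporting levels for immunogenicity as "flavivirus-seropositive, flavivirus-seronegative groups, flavivirus-serostatus missing, and overall".

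The one model for antibody titres is the Day 57 ANCOVA in SAP 6.4.2. It "will be carried out for flavivirus-seropositive groups and flavivirus-seronegative groups separately using the PP Set", "with the vaccination group as a factor and the baseline values as covariate", and the baseline covariate applies to seropositives only. There is no pooled version and no region term.

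SAP 4.4 states that under Amendments 1 to 3 "randomization will be stratified only by" region (continental US or Puerto Rico). Under the original protocol the stratum was serostatus by a point-of-care test. In the immunogenicity analysis region has only an optional role: subgroup analyses by age group, "gender and region may be performed". By contrast, SAP 6.3.1.5 firmly plans region subgroups for solicited reactions.

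Protocol 4.3 anticipates that response may differ by baseline serostatus. Protocol 5 assumes that most seronegatives will come from the continental US and most seropositives from Puerto Rico. SAP 4.2 states that no hypothesis is tested.

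**The concern.** The Day 57 PRNT GMT in all participants is a primary endpoint (SAP 3.1), and the primary objective is a comparison with placebo (SAP 2.1). The only planned ratio for all participants is the unadjusted one. If titres differ between seropositives and seronegatives, as the protocol anticipates, a pooled t-interval counts that spread as noise. A model containing serostatus and the randomisation stratum would remove it.

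The trial reports intervals rather than tests, and SAP 6.6 makes the interim results the basis for moving to Phase 3. A tighter overall estimate at no extra data cost is therefore worth having. What is at stake is the width of the interval, not its validity.

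**Working it through.** **The plan's own figure.** Protocol 9.2 states about 90% power for a 4-fold difference but gives no SD, so the figure cannot be reproduced. Inverting it (two-sided 5%, log10 4 = 0.602) gives SD = 0.602 / [(1.96 + 1.282) × √(2/n)]. That is 1.31 at n = 100 per arm and 1.86 at n = 200. At SDs of 0.4 to 1.0 the power is 98.9% or more. The documents therefore do not settle the SD.

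**Inputs.**
- From the documents: 200 per arm, about half seropositive (SAP 4.1).
- Assumed: within-stratum log10 SD 0.6; region agrees with serostatus in a = 0.8 of participants; serostatus gap g = 0, 0.5 or 1.0 log10.

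**Gap common to both arms.**
- Unadjusted SD = √(0.36 + 0.25g²) = 0.600, 0.650, 0.781.
- Region-adjusted SD = √(0.36 + a(1−a)g²) = 0.600, 0.632, 0.721.
- Serostatus-adjusted SD = 0.600.
- Width ratio, unadjusted to serostatus-adjusted: 1.000, 1.083, 1.302.
- Width ratio, unadjusted to region-adjusted: 1.000, 1.028, 1.083.

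**On the fold scale.** The lower limit at an observed 4-fold ratio is 4 / 10^(1.96 × SD × √(2/200)):

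| Gap (log10) | Unadjusted | Region | Serostatus |
|---|---|---|---|
| 0 | 3.05 | 3.05 | 3.05 |
| 0.5 | 2.98 | 3.01 | 3.05 |
| 1.0 | 2.81 | 2.89 | 3.05 |

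**Gap in one arm only, main-effects serostatus model fitted to all four arms.** The common slope is g/4.
- Unadjusted variance, summed over the vaccine arm and placebo: 0.72 + 0.25g².
- Adjusted: 0.72 + 0.25(3g/4)² + 0.25(g/4)² = 0.72 + 0.15625g².
- g = 0.5: √(0.7825/0.7591) = 1.015. g = 1.0: √(0.970/0.876) = 1.052.
- The sum, and so the ratio, is the same if all three vaccine arms show the gap and placebo does not.
- Region alone as a main effect gives 1.007 and 1.019 by simulation.

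**Sensitivity (common gap).**
- At g = 0.5 with SD 0.4 or 0.8, the serostatus ratio is 1.179 or 1.048.
- Over the same SDs, with agreement from 70% to 95%, the region ratio runs from 1.007 to 1.138.
- With the SDs of 1.31 and 1.86 implied by the power statement, √(SD² + 0.25g²)/SD is 1.02 and 1.01 at g = 0.5, and 1.07 and 1.04 at g = 1.0.

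**Validity.** Under region-stratified allocation the unadjusted interval covers 95.0%, 95.6% and 96.6% at g = 0, 0.5 and 1.0. Simulations of a main-effects pooled model with robust standard errors gave coverage of 94.0-96.3%, and it was essentially never wider than the unadjusted interval.

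**Region inside the serostatus-specific ANCOVAs.** For a regional gap of 0, 0.3 or 0.5 log10, √(0.36 + a(1−a)g²)/0.6 is 1.000, 1.020, 1.054 at a = 0.8 and 1.000, 1.006, 1.016 at a = 0.95.

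**The case against.** The strongest reply is that nothing here is an error. An unadjusted GMR is a legitimate descriptive summary, no hypothesis is tested, and the Day 57 ANCOVA already conditions on serostatus by fitting each stratum separately. If response differs by serostatus, the stratum-specific ratios are arguably the more useful results. SAP 6.1 speaks of serostatus groups and/or overall, which leaves some latitude on the overall level. All of this stands, and it keeps the point minor. It does not supply an adjusted ratio for the all-participant endpoint.

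It also stands that every size above rests on inputs the documents do not give, and that the 8% and 30% figures need the same gap in vaccine and placebo.

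Three stronger readings are tempting, and the documents do not support them:
- A reader might infer that ignoring the randomisation stratum makes the interval invalid. It does not: coverage is nominal or slightly above.
- A reader might infer that the missing region term is the main loss. Region alone gains 0, 3 or 8% with a common gap and about 1-2% with a one-arm gap; most of the gain comes from serostatus.
- A reader might extend the point to cellular immunity. SAP 6.4.5 says of those endpoints that "the analysis details will be provided in a separate document", so nothing can be concluded about them.

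One might also want an arm-by-serostatus interaction in the pooled model. With an unknown serostatus category, that interaction cannot be estimated if any arm has no unknowns. At assumed unknown rates of 2%, 1% and 0.5%, the chance of this, 1 − [1 − (1 − p)^200]^4, is 7%, 44% and 84%. A standardised version of such a model also had coverage down to about 94% when the gap was in the vaccine arm only.

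**Conclusion.** The point holds as a modest gain in precision. The SAP has no adjusted all-participant GMT ratio versus placebo, and the overall GMR interval is unadjusted. That interval is valid and at worst conservative.

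Its excess width depends on how far titres differ by serostatus, in which arms, and against what SD. Under the stated assumptions the excess runs from nothing to 30% with a common gap, and is about 1-5% against a main-effects model with a one-arm gap. At larger SDs it shrinks further. Even in the widest case shown, the lower limit at a 4-fold ratio is 2.81, far above 1, so no vaccine-placebo conclusion at that effect would change. Confidence is high in the reading of the text and low in any single figure for the gain.

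**What to change.** Add to SAP 6.4.3 a supportive pooled model of log10 PRNT titre in the PP Set, at Day 57 and at the other GMR time points:
- Terms, as main effects: vaccination group, baseline laboratory serostatus (negative, positive, unknown) and region.
- Robust standard errors.
- Output: the overall GMT ratio of each mRNA-1893 arm versus placebo with its 95% CI.

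Do not add an arm-by-serostatus interaction to this model. The serostatus-specific ANCOVAs already show the stratum-specific ratios. Keep the unadjusted GMTs and GMRs as descriptive results. Adding region to the two serostatus-specific ANCOVAs is optional, since the gain there is 0-5% under the same assumptions.

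The cost is SAP wording and programming. Region and laboratory serostatus are already collected, and region is already used in the solicited-reaction tables. No participants, visits or samples are added.
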